**ID:** 9R44MH117956-02

**Title:** PlusCare: Mobile Platform to Increase Linkage to Care in Adolescents Living With HIV/AIDS

**NCT ID:** NCT03758066

**Date of Protocol:** 3/15/2018

**Dates Approved by Sites:** 1/2/2019 (BCH) and 2/01/2019 (BMC)

**Study Objective and Overview:** To conduct a mixed-methods, non-randomized pre-post study to test PlusCare, a mobile application, in real-world clinical settings. In a Phase I project, members of the research team demonstrated the acceptability and feasibility of PlusCare, a mobile application system developed by Dimagi, Inc. to support HIV case management for youth living with HIV (YLH) aged 13 to 25 years old. In this Phase II SBIR project, we will enhance the PlusCare system to best serve the team-based care delivery model identified in Phase I and test it in a non-randomized, pre-post intervention study conducted in multiple clinical settings. The objective of this Phase II project is to test and demonstrate the effectiveness of PlusCare on HIV case management process and care continuum outcome measures.

**Study Design:** Patients and case managers (CMs) will be recruited from three HIV case management programs in two hospitals in the metro Boston area. Patients will use the PlusCare application for 12 months, while CMs will use the system for at least 15 months in order to account for rolling patient recruitment (i.e., 3 months to enroll target number of patients). We will perform a process and outcomes evaluation of the system to determine the effect of the PlusCare intervention on HIV health status and case management outcomes.

**Patient Selection and Inclusion/Exclusion Criteria:** A research assistant (RA) will recruit CMs (N=20) and patients (N=50).

The patient eligibility criteria are as follows:

*Inclusions:*

- 1) between 13-25 years old,
- 2) patient of the BCH HAPPENS or BCH CHAP program,
- 3) HIV-positive,
- 4) own or ability to access a smartphone (e.g., iPhone, Android) for one year, and
- 5) be in care for at least 1 year prior (for access to historical control data)

*Exclusions:*

- 1) Non-English speaker or
- 2) Visually or hearing impaired

These criteria were selected to ensure the focus and inclusion of YLH to fulfill the purpose and function of this proposed application for case management to serve this population, who most benefit from the support for care and services that the case management model provides. Additionally, our team wanted to ensure that the patients would be able to run the PlusCare app on their device for the needed length for the study.

The CM eligibility criteria are as follows:

*Inclusions:*

- 1) are actively employed BCH and
- 2) perform case management duties with HIV-positive patients 13-25 years old

**Description of Study Treatments or Exposures/Predictors:** Study participants will be given a username and access to the PlusCare app on their own personal devices. CMs will have access to the mobile app available on a study tablet that will be provided to each program or web app accessible from their own work computers.

**Definition of Primary and Secondary Outcomes/Endpoints:** Primary outcomes will be CD4 count, viral load, and HIV medical visit frequency. Secondary outcomes include emergency room visits and hospitalizations, adherence, patient reported quality of life, system usage data (such as log-ins) and system usability and satisfaction. This is detailed further in the table below:

Patient Measures	Pre	Post		Data Source
	1-year prior	Base	6-mos	
Baseline Demographics				
Current gender  , sexual orientation identity (BRFSS  ), age/date of birth, income & employment (STRIVE  ), years since diagnosis, time spent in case management, housing stability, insurance, retention and quality of care, treatment		x		Survey, EHR
Experience with Technology		x		Survey
Primary Outcomes				
CD4, viral load 	x	x	x	EHR (Lab data)
HIV medical visit frequency and gaps 	x	x	x	Billing data, EHR
Secondary Outcomes				
ED visits, hospitalizations	x	x	x	Billing data, Survey
Patient-centered: Quality of Life (CDC HRQOL-14), self-efficacy (based on chronic disease scale)	x	x	x	Survey
System: Usage (log in frequency, dwell time)		x		System data
System: Usability and Satisfaction 		x		Survey

**Data Collection Methods, Assessments, Interventions and Schedule (what assessments performed, how often)**

For case managers:

*Baseline assessment and in-person training.* Enrolled CMs will attend an in-person training session, which will be led by a RA with a Dimagi study team member with technical experience in the development of PlusCare. A baseline survey will be administered to collect basic demographic data (e.g., age, sex, race, ethnicity, education), information on professional role and experience (e.g., job title, years of CM experience, number of patients managed), and experience with technology. In the training session, Ease of training and feasibility of this model of patient registration will be assessed in this study through qualitative feedback collected from CMs at the end of the study.

*Intervention.* All CMs will have access to PlusCare via mobile app installed on a study tablet or web app accessible from any computer for at least a period of 15 months to accommodate for rolling patient enrollment. During this study period, data on CM usage of PlusCare will be collected passively through the tablet as well as through web app access and outputted as daily usage logs.

*End-of-Study Interview with CMs.* Towards the end of the study period (i.e., 15 months after Baseline), CMs in each program will be re-contacted by the respective study RA at each site to participate in a one-hour focus group. Focus groups will comprise 2-8 participants and will be led by the study RA in a private setting. For those who are unable to attend a scheduled focus group, a separate structured one-on-one interview will be scheduled.

*CM participant compensation.* CMs will be compensated \$50 for completing the Baseline Assessment and Training Session and \$100 for completing the End-of-Study Interview. If a CM drops out of the study before the end of the study due to circumstances unrelated to the study (e.g., change in employment), s/he will still have an opportunity to participate in an end-of-the-study interview and will receive \$100 for completion of that study activity. Any CMs who are newly employed during the 15-month period will be recruited to participate in the study and compensated in the same fashion.

For patients:

*In-person baseline interview.* Upon receiving written assent or consent, the RA will then proceed to administer a baseline assessment and a semi-structured, open-ended interview. The RA will be responsible for registering the patient into the PlusCare system and setting up the patient's contacts. A parent handout about the study will be prepared for distribution to patients who wish to share information with a parent about the study. All patients will install the PlusCare application on their own smartphone, with assistance from the RA if needed. Once PlusCare has been installed and the patient has successfully demonstrated that s/he can 1) access the app from his/her smartphone and 2) receive incoming SMS messages from the CM, the patient will be actively enrolled for one year.

*Intervention.* All patients enrolled in the study will have access to all of PlusCare's functionalities for a period of at least 12 months starting from the time they are enrolled. App activity will be monitored throughout the 12-month period.

*Monthly Adherence Assessment.* A validated one-item medication adherence assessment will be administered once a month; this assessment consists of patients' self-reported rating of their perceived ability to take all of their medications as prescribed in the past month. Patients will receive an SMS message alerting them to submit a response to the adherence assessment from within the PlusCare app, thus ensuring individuals' responses remain confidential. While the method of self-report may be subject to recall and social desirability bias

compared to other more objective measures such as digital medicine systems or pharmacokinetic measures, it has the advantage of being feasible and acceptable and less susceptible to misestimation due to device non-use and pocket dosing or overestimation due patients opening the device without removing pills. Based on findings from adherence studies, including our previously funded SBIR project (ARemind), adherence reminders are effective in collecting timely, reliable measures of adherence and we recognize that there is a potential that they may be associated with a decrease in HIV-1 RNA viral load.

*Retrospective data.* The study RA will access key variables of interest from the patient's electronic case management records (via PowerChart) and administrative and hospital billing data dating back 1 year from date of enrollment for initial cost-effectiveness analysis that will contribute to the evaluation and commercialization plan. Key variables will include viral load and CD4 counts from lab results and medical visit frequency and gaps consistent with standards for Ryan White Foundation-funded programs.

*6-Month and 12-month Follow-up Assessment.* At the 6-month and 12-month time point, the site RA will contact each patient to complete assessment items online. The RA will disseminate an online survey to the patient. Responses will be collected via a CommCare survey form and stored in the CommCare server. Patients will have the option of completing this assessment in person if they prefer, but compensation will remain the same as a remote assessment.

*Safety plan.* Before completing the surveys potential participants will read and sign an informed consent. This form will document a potential participant's understanding that if they identify any level of emotional distress above baseline on survey questions, the results will be flagged and e-mailed to a member of the study team. Participants will subsequently be contacted by the study team member or another mental health provider within two business days to have a safety check-in. No items have explicit safety concerns such as suicidality. We will also document a potential participant's understanding that if we identify during surveys/screening any heavy or dangerous use of substances in the past 30 days, we will report the use to their provider for safety. Participants will be given a mental health resource list at the time of consent in case they experience emotional distress at any point throughout the course of the study.

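### The default setting for the quality-of-life and self-efficacy surveys moves from in person with the RA at baseline to remote online at 6 and 12 months, and the plan neither records nor analyses mode

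*Combined protocol and SAP*

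**What the plan says.** **Baseline.** In the data collection section for patients, under the item headed "In-person baseline interview", "the RA will then proceed to administer a baseline assessment and a semi-structured, open-ended interview". The assessment and the open-ended interview are listed as two things. The text does not say whether the assessment items are read aloud or filled in by the patient with the RA present.

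**Follow-up.** "At the 6-month and 12-month time point, the site RA will contact each patient to complete assessment items online". The next sentence is "The RA will disseminate an online survey to the patient", and answers go onto a CommCare form. There is an alternative: "Patients will have the option of completing this assessment in person if they prefer". Compensation is the same either way.

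**Outcomes affected.** The measures table under the definition of outcomes lists "Quality of Life (CDC HRQOL-14), self-efficacy (based on chronic disease scale" as secondary, with a survey as the only data source. CD4 and viral load come from EHR laboratory data, and medical visits from billing data and the EHR.

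**Analysis.** The SAP names a Wilcoxon test of pre against post, a repeated measures analysis, and mixed effects modelling with time-variant and time-invariant factors that it does not list. Nowhere do the documents say that completion mode is recorded, held constant, adjusted for or examined in a sensitivity analysis.

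**The concern.** Answers about health, mood and confidence in managing one's condition can differ between a session with a staff member and a private screen. The protocol itself accepts that self-report is open to social desirability bias, and it routes the monthly adherence item through the app to keep answers confidential. Its safety plan adds a possible reason for guarded answers: reported distress leads to contact from the study team, and heavy substance use is reported to the provider. Respondents are aged 13 to 25 and living with HIV.

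The study is a non-randomized pre-post design. With no concurrent group followed through the same change of setting, nothing cancels a shift. The default setting changes between the pre and post values, so a shift could be read as a PlusCare effect or could hide one. Because patients choose the follow-up setting, those seen in person may also differ from those who answer online. If the setting is not recorded, the question cannot be examined afterwards.

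**Working it through.** The plan gives no figure on survey mode. Its one calculated figure, 81% power for a 38% change in log10 viral load, concerns a laboratory outcome and plays no part here.

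**1. The time points side by side**

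| | Baseline | 6 and 12 months |
|---|---|---|
| Default setting | In person, RA administers | Remote, online survey |
| Alternative | None stated | In person, patient's choice |
| Items read aloud or self-completed | Not stated | Self-completed online; not stated for in person |
| Mode recorded | Not stated | Not stated |

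The change of default setting is documented. A change from interviewer-read to self-completed items is possible but not stated. Because of the in-person alternative, setting and period overlap without coinciding completely.

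**2. What a shift could do**

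Inputs from the documents: N = 50 (power section), and two-sided 5% (SAP). Assumed, because the documents give nothing: a shift m of 0.1, 0.2 or 0.3 SD of the score; within-person correlation ρ of 0.5 or 0.7; share switching p of 1 or 0.5; no true change; complete pairs. A paired t-test stands in for the Wilcoxon test.

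- Mean change = p·m
- SD of change = √[2(1 − ρ) + m²·p(1 − p)]. The second term is the extra spread when only some patients switch.
- d = mean change / SD of change; noncentrality = d·√50
- False-positive rate = probability that |t| exceeds 2.01 on 49 degrees of freedom

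Example, all switch, m = 0.2, ρ = 0.5: SD = √1 = 1, d = 0.2, noncentrality 0.2 × 7.07 = 1.41, rejection probability 28.4%.

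Example, half switch, m = 0.3, ρ = 0.7: mean 0.15, SD = √(0.6 + 0.09 × 0.25) = 0.789, d = 0.190, noncentrality 1.34, rejection probability 26.1%.

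| Share switching | ρ | m = 0.1 | m = 0.2 | m = 0.3 |
|---|---|---|---|---|
| All | 0.5 | 10.7% | 28.4% | 54.8% |
| All | 0.7 | 14.6% | 43.3% | 76.6% |
| Half | 0.5 | 6.4% | 10.6% | 17.7% |
| Half | 0.7 | 7.3% | 14.4% | 26.1% |

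The nominal rate is 5%. A lower correlation reduces the figures: at ρ = 0.3 they are 9%, 22% and 42% if all switch, and 6%, 9% and 14% if half do.

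**The case against.** A reader might infer four stronger things, and the documents support none of them.

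- **That the RA interviews patients for these items at baseline.** Only the open-ended part is called an interview. The protocol also uses the word administered for the monthly adherence item, which patients answer themselves in the app. The safety plan speaks of participants completing the surveys. Self-completion with the RA present fits the text.
- **That follow-up is almost always online.** Online is the default, but in-person completion is offered for equal compensation and no uptake figure is given.
- **That no model could separate mode from period.** With an in-person option they do not fully coincide, and a mixed model with time-variant factors could carry a mode term. The accurate statement is that none is named.
- **That bias has been shown.** The documents give no size or direction for a shift. The 77% figure needs the largest assumed shift, the higher correlation and every patient switching, all at once.

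It is also fair to say that these are secondary outcomes in an openly uncontrolled study, so a change could not be attributed securely to PlusCare even with a constant mode.

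What remains is more than a missing detail. Followed as written, the plan produces a mixture of settings chosen by the patients, on top of a default that changes at the pre-post boundary. Any mode effect would be an avoidable bias, separate from the lack of a control group.

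**Conclusion.** The point holds as a risk of bias of unknown size and direction. It is limited to quality of life and self-efficacy, and to the survey part of emergency department visits and hospitalizations, which also have a billing source. The primary outcomes are untouched, as is the monthly adherence item, which stays in the app throughout.

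At correlations of 0.5 and 0.7, the illustrated false-positive rates run from 11% to 77% if every patient changes setting and from 6% to 26% if half do. They rest on assumed shifts, correlations and uptake, and on 50 complete pairs. At the low end, a 0.1 SD shift with half switching, little is added to the nominal 5%. The change is worth making because it is cheap and removes a possible source of bias that the analysis plan does not address.

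**What to change.** 1. In the baseline and follow-up items of the data collection section, state that patients self-complete the same CommCare survey form at baseline, 6 months and 12 months. At baseline this comes before the open-ended interview. In-person follow-up stays available, on that same form.
2. Record mode and setting (remote, or RA present) at every assessment.
3. In the SAP, prespecify a sensitivity analysis for quality of life and self-efficacy, either with a mode or setting term in the mixed model or restricted to patients in the same setting throughout. Because patients choose the setting, both versions should be read as supportive only.

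**Cost.** A few sentences, one recorded field and one extra analysis, with no change in sample size. The plan already calls for a CommCare form at follow-up, so baseline would use the same one. The RA has less opportunity to clarify items at baseline. A common form does not fully equalise RA presence between baseline and remote follow-up, which is why the setting must still be recorded.

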### **Statistical Analysis Plan**

The study analysis will follow an *intention-to-treat* approach to determine PlusCare's effect on outcomes related to HIV case management. Our primary outcomes will include Ryan White Program core performance measures (HIV viral suppression, HIV medical visit frequency, and gaps in medical visits). Secondary outcomes will include proximal outcomes (medication adherence), patient-centered outcomes (quality of life, self-efficacy), and system usage and usability. Usage data collected passively from the system from both patients and CMs will be analyzed to assess trends in system usage (e.g., what module was accessed by patients most frequently, how many documents were sent by CMs) and system usability will be assessed via the SUS administered at the end of the study. Baseline characteristics of our sample were summarized with descriptive statistics (mean, median, SD, frequency) and a Wilcoxon test for significance will be used to assess PlusCare's impact on our outcomes of interest pre- and post-intervention and a repeated measures analysis will be used to determine changes in outcomes assessed at each respective time point during pre- and post-intervention. Under the

assumption that some individual specific effects are uncorrelated with the independent variables while some other effects are correlated, we will use mixed effects modeling to account for both time-variant and time-invariant factors. Initial cost-effectiveness analysis will be performed following methods used in previous studies. Data on HIV medical visit frequency and gaps and ED visits and hospitalizations will be used to perform this analysis. The monetary benefit from the PlusCare intervention arises from the cost savings as a result of reduction in hospital visit frequency between pre- and post-intervention. We will compute preliminary cost-effectiveness of the PlusCare intervention by comparing the cost savings attained with the program cost of the case management program using Net Present Value (NPV = *Present Value of Cost Savings – Present Value of Program Costs*) and the Return on Investment (ROI = *Present Value of Cost Savings / Present Value of Program Costs*). We hypothesize that the use of PlusCare will have a positive effect on the return on investment. All statistical analyses were performed using R statistical software (R Foundation for Statistical Computing, Vienna, Austria) or SAS software, version 9.2 (SAS Institute, Cary, NC) and a two-tailed P-value of the test < 0.05 was considered statistically significant.

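### ED visits and hospitalizations feed the savings, NPV and ROI but are missing from the SAP's outcome lists, and NPV and ROI are planned without any measure of uncertainty

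*Combined protocol and SAP*

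**What the plan says.** **Protocol, Definition of Primary and Secondary Outcomes/Endpoints.** The text reads "Secondary outcomes include emergency room visits and hospitalizations, adherence, patient reported quality of life", followed by the system measures. The measures table repeats the item ("ED visits, hospitalizations") under Secondary Outcomes, marks it in both the pre and the post columns, and gives billing data and survey as the source.

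**Statistical Analysis Plan, outcome lists.** The primary outcomes are viral suppression, medical visit frequency and gaps in visits. For the secondary outcomes: "Secondary outcomes will include proximal outcomes (medication adherence), patient-centered outcomes (quality of life, self-efficacy), and system usage and usability". ED visits and hospitalizations appear in neither list.

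**Statistical Analysis Plan, methods.** Two general statements follow. The first is "a Wilcoxon test for significance will be used to assess PlusCare's impact on our outcomes of interest pre- and post-intervention". The second plans a repeated measures analysis of change across the pre and post time points. Neither says which outcomes it covers.

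**Statistical Analysis Plan, cost analysis.** The inputs are given as "Data on HIV medical visit frequency and gaps and ED visits and hospitalizations will be used to perform this analysis". The monetary benefit is the "cost savings as a result of reduction in hospital visit frequency between pre- and post-intervention". NPV is the present value of savings minus that of program costs, and ROI is the ratio of the two. The plan hypothesizes a positive effect on ROI. It calls the analysis initial and preliminary, and it states no interval, test or sensitivity analysis for NPV or ROI.

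**The concern.** An outcome that the protocol defines, and that the economic result uses, drops out of the list from which an analyst would work. The analyst must then guess whether the general test applies to it and whether an effect estimate is expected.

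The economic result has the same gap one step further on. A pre/post difference in hospital use among about 50 patients is turned into money and compared with program costs, and nothing in the plan shows how much of that difference could be chance. The Retrospective data section says that the cost work will feed the evaluation and the commercialization plan, so the figure will be used to support decisions. A single NPV or ROI would look firmer than the data behind it.

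**Working it through.** **Step 1. The sections side by side.**

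| Place | ED visits and hospitalizations |
|---|---|
| Outcome definitions, text | Named as secondary |
| Outcome definitions, table | Listed under Secondary Outcomes, pre and post |
| Retrospective data, key variables | Not named |
| SAP, primary list | Not named |
| SAP, secondary list | Not named |
| SAP, Wilcoxon and repeated measures | Outcomes not itemised |
| SAP, cost analysis | Named as an input |
| Statistical Power and Sample Considerations | Not addressed (viral load only) |

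The plan gives no figure for this outcome that could be reproduced. Its one computed figure, 81% power, concerns log10 viral load. It corresponds to a paired standardized change of (1.960 + 0.878)/√50 = 0.401. No SD is given to check it further, and nothing below depends on it.

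**Step 2. How often would events fall by chance?**

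Inputs from the documents: 50 patients, one year of retrospective data, and 12 months of app use. Assumptions, because the documents give no event rates: r = 0.3, 0.5 or 1.0 events per patient-year, the same in both years, and complete data.

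Let X be the total count before and Y the total count after. Under Poisson counts with no effect, both have mean 50r. Two probabilities are wanted: P(Y < X), and P(Y ≤ 0.8X) with X > 0, which is a fall of 20% or more. Both are obtained by summing the joint Poisson probabilities.

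| r | Mean events per year, 50r | SD of X − Y, √(2 × 50r) | P(any fall) | P(fall of 20% or more) |
|---|---|---|---|---|
| 0.3 | 15 | 5.5 | 46.3% | 28.1% |
| 0.5 | 25 | 7.1 | 47.2% | 22.3% |
| 1.0 | 50 | 10.0 | 48.0% | 13.7% |

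A 20% fall is 3, 5 or 10 events, that is 0.55, 0.71 or 1.0 SD of the difference.

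**Step 3. Overdispersion.** Patients differ in how often they use hospital care, but the same patients are counted in both years. With a gamma patient effect shared across the two years (shapes 0.5, 1 and 2), the share with a fall of 20% or more is about 28%, 22-23% and 14%, essentially the Poisson values. Higher shares arise only if each patient's propensity is redrawn between the years, and they are not used here.

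**Step 4. If the general Wilcoxon test does apply.** With 50 patients, a shared gamma effect of shape 1 and assumed rates of 0.3 to 2.0 per year, a paired Wilcoxon test has about 11% to 42% power for a 25% reduction and 32% to 97% for a 50% reduction. A p-value alone would say little about a modest change. An interval shows what the data can and cannot exclude.

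**Step 5. From events to money.** NPV > 0 requires the present value of savings to exceed that of program costs, which is the same condition as ROI > 1. A fall in events is necessary for savings from that source but is not enough for a favourable NPV. Unit and program costs are not in the documents, so the probabilities in Step 2 cannot be converted into a probability of a favourable NPV.

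**The case against.** A reader might infer that no test is planned for ED visits and hospitalizations, and that the cost analysis therefore rests on an untested difference. The documents do not support that. Protocol and SAP form one short document, the protocol part makes these secondary outcomes, and the SAP's general methods are not confined to the listed items. The SAP list need not be exhaustive and excludes nothing. The plan ties no named method to almost any individual outcome. A pre/post test of hospital use may well be intended.

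It would also be too strong to call ED visits and hospitalizations the sole source of the savings. HIV medical visit frequency and gaps are inputs too, and they are SAP primary outcomes. Hospital visit frequency is not defined. Equating it with ED visits and hospitalizations is the natural reading, since a program of this kind would hope to maintain or raise HIV visits, but the plan does not say so.

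Nor does the plan take a reduction for granted. It describes how a benefit would arise, states a hypothesis, and labels the analysis preliminary. The costing methods are referred to cited studies, which may deal with uncertainty but cannot be consulted here. Finally, a chance fall in just under half of null trials is true of any pre/post difference and is not peculiar to this trial.

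All of this stands. What it leaves untouched is the mismatch between the two outcome lists, the undefined savings term, and the absence from the plan itself of any uncertainty for NPV and ROI. Even if the Wilcoxon test covers hospital use, its result is not linked to the savings calculation.

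**Conclusion.** The point holds as an inexpensive improvement. The protocol and SAP outcome lists disagree on ED visits and hospitalizations, no analysis is explicitly tied to that outcome, and NPV and ROI are planned as point values despite a hypothesis about ROI.

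The size is illustrative: chance falls in about 46-48% of null trials, and falls of 20% or more in about 28%, 22% and 14%. These figures rest on 50 patients, one year on each side, complete data, assumed rates of 0.3, 0.5 and 1.0 per patient-year, and Poisson counts or a patient effect shared across years. They describe event totals. They are not the chance of a favourable NPV, and they do not show that the outcome will go untested.

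**What to change.** 1. Add ED visits and hospitalizations to the secondary outcomes in the Statistical Analysis Plan, so that it matches the protocol's outcome definitions and table.
2. State that the planned pre/post test applies to them, and report the pre/post change with a 95% confidence interval alongside it.
3. Define hospital visit frequency in the cost analysis: which visit types count towards savings, and how HIV medical visits enter.
4. Report NPV and ROI with a 95% interval from a bootstrap that resamples patients, keeping each patient's pre and post data together. Describe savings as preliminary when the NPV interval includes 0 or the ROI interval includes 1.

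The cost is a few lines of SAP text and one short extra analysis, with no data beyond those already planned. The economic result will look less certain.

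### The cost-effectiveness savings term is undefined and, as worded, can count lost HIV medical visits as savings, against a primary outcome

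*Combined protocol and SAP*

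**What the plan says.** The Statistical Analysis Plan names the inputs to the cost-effectiveness analysis: "Data on HIV medical visit frequency and gaps and ED visits and hospitalizations will be used to perform this analysis". It then defines the monetary benefit as "cost savings as a result of reduction in hospital visit frequency between pre- and post-intervention". NPV is "Present Value of Cost Savings – Present Value of Program Costs", and ROI is the ratio of the same two terms. The cost term is the "program cost of the case management program". No unit costs, program cost or discount rate are given.

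HIV visits are also a primary outcome. The section on primary and secondary outcomes says "Primary outcomes will be CD4 count, viral load, and HIV medical visit frequency", and the Statistical Analysis Plan lists "HIV viral suppression, HIV medical visit frequency, and gaps in medical visits". The title states the direction intended: "Mobile Platform to Increase Linkage to Care in Adolescents Living With HIV/AIDS".

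Three other places bear on the point:
- **Study Design:** patients come from "three HIV case management programs in two hospitals in the metro Boston area".
- **Outcome table:** HIV visits are sourced from billing data and the EHR; ED visits and hospitalizations are sourced from billing data and survey.
- **Inclusion criteria:** patients must have been in care for at least the year before entry. Nothing similar applies afterwards.

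**The concern.** The intervention is meant to keep young people in HIV care, so a good result is more HIV visits and fewer gaps. If an HIV clinic visit at a hospital counts as a hospital visit, a patient who stops attending adds to the savings. The economic result could then look favourable partly because patients disengaged.

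The entry criterion makes this one-directional. A patient may have missed visits in the year before enrollment, but complete departure from care cannot fall there; it can fall only in the post period. The plan has no rule for patients who leave care or leave the site's billing system.

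The plan hypothesizes a positive effect on ROI, and the Retrospective data paragraph says that the cost-effectiveness analysis will contribute to the evaluation and commercialization plan. A reader of that ROI could not tell avoided acute care from lost HIV care.

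**Working it through.** The plan states no figure for this analysis, so there is none to reproduce. The check has two parts: what the wording allows, and how the result moves under each reading.

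**1. What the wording allows**

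- NPV and ROI have two terms. Program costs are those of case management, so savings is the only term left for HIV visit data to enter.
- Among the care measures, visit frequency is used elsewhere in the document only for HIV medical visits, never for ED visits or admissions.
- The Retrospective data paragraph obtains hospital billing data for the cost-effectiveness analysis. Its key variables include medical visit frequency and gaps; ED visits and admissions are not named there.
- On the other side, the plan names HIV medical visits, ED visits and hospitalizations separately. Hospital visits could be shorthand for the last two.

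Both readings fit the text.

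**2. How the result moves**

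Let V, E and H be HIV visits, ED visits and hospitalizations per patient-year, with unit costs cV, cE and cH. For N patients,

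S = N × [cE(Epre − Epost) + cH(Hpre − Hpost) + L × cV(Vpre − Vpost)], ROI = S / P, NPV = S − P.

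L = 1 if HIV visits count as hospital visits; L = 0 if they do not. P is the program cost. Discounting is ignored.

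N = 50 is from the document. Everything else is assumed: Vpre = 4, Epre = 0.5, Hpre = 0.1; cV = 1, cE = 3, cH = 30 units; P = 50 units.

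| Scenario | S, L = 1 | ROI, L = 1 | S, L = 0 | ROI, L = 0 |
|---|---|---|---|---|
| A. 20% lost; only their HIV visits vanish (Vpost = 3.2) | 50 × 0.8 = 40 | 0.8 | 0 | 0.0 |
| B. 20% lost; all their billed contacts vanish (Vpost = 3.2, Epost = 0.4, Hpost = 0.08) | 50 × (0.3 + 0.6 + 0.8) = 85 | 1.7 | 50 × 0.9 = 45 | 0.9 |
| C. One more HIV visit each; ED visits and admissions unchanged | 50 × (−1) = −50 | −1.0 | 0 | 0.0 |
| D. One more HIV visit each; ED visits and admissions down 20% | 50 × (0.3 + 0.6 − 1) = −5 | −0.1 | 50 × 0.9 = 45 | 0.9 |

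- A is the fault: under L = 1, disengagement alone yields an ROI of 0.8.
- B and D give the same ROI of 0.9 under L = 0. Restricting the savings term does not by itself separate true success from patients who vanish from billing.
- Under L = 1, with one added visit each, a proportional fall f in ED visits and admissions gives S = 50 × (4.5f − 1), which is positive once f exceeds 1/4.5 = 22%. More HIV visits need not mean a poor ROI.

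**3. In dollars, on assumed prices**

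At 4 visits a year, a patient who leaves after 3 months loses 3 visits. Five such patients lose 5 × 3 = 15 visits; at $200 to $600 each, $3,000 to $9,000 is booked as savings.

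**The case against.** The strongest reply is that the text does not say a missed HIV visit is money saved. Hospital visits may mean ED visits and admissions, and a gap in visits has no obvious unit cost, which suggests that HIV visit data may serve another purpose. The plan also defers to methods of earlier cost studies, which may define the costed encounters; they are not available here. This stands to the extent that the perverse result is one reading and not a certainty. It does not remove the problem, because the plan itself neither defines the term nor says how HIV visits enter.

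Three stronger inferences are tempting and not supported:
- **That success on the visit outcome necessarily lowers ROI.** This needs L = 1, and even then a large enough fall in acute care outweighs it. Charging added visits is also proper accounting: moving them from negative savings to cost leaves NPV unchanged.
- **That the sign of NPV turns on this alone.** In scenario B, NPV is 85 − 50 = +35 under L = 1 and 45 − 50 = −5 under L = 0, but only because P was set between 45 and 85. The documents give neither program cost nor acute-care savings.
- **That the trial's main conclusions are at risk.** The plan calls the cost analysis initial and preliminary. Visit frequency and gaps are analysed in their own right as primary outcomes, where loss from care should be visible.

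**Conclusion.** The point holds as a defect of definition with a harmful possible consequence. As worded, the cost-effectiveness rule can credit lost HIV visits as savings, and the entry criterion places complete loss from care in the post period. It rests on hospital visits being read to include HIV clinic visits, which the wording and data sources allow but do not compel. A second route remains under either reading: patients who leave the site may also lose billed ED visits and admissions.

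The size cannot be established from the documents. On assumed inputs, 20% loss from HIV care with nothing else changed moves ROI from 0.0 to 0.8. The point concerns a preliminary analysis and its use in the commercialization plan; the primary outcome tests are unaffected. It should be corrected before NPV and ROI are computed.

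**What to change.** In the cost-effectiveness text of the Statistical Analysis Plan:

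1. Define the savings term as the pre-to-post change in the cost of ED visits and hospitalizations only, and take HIV medical visits and gaps out of it.
2. Report the change in HIV medical visits and its cost separately, beside NPV and ROI.
3. Add a sensitivity analysis that costs HIV visits symmetrically, increases and decreases alike, read beside the visit change. Charging increases while ignoring decreases would add bias if applied per patient. With Poisson visits of mean 4 in both years and no true change (an assumption), the expected positive part is 1.11 visits per patient. That is 1.11 × 50 = 55.5 visits, or $11,100 to $33,300 of false cost at $200 to $600 each.
4. For patients who leave the site, use the survey data on ED visits and hospitalizations, and repeat NPV and ROI in patients with complete post-period follow-up. Patients who leave may not answer the survey, and those with complete follow-up are a selected group, so this is a sensitivity analysis only.

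The cost is a change of wording and some added analysis on data already planned. The downside is that the stated ROI may be less favourable.
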